# **6.9.2** Special Considerations for Corticosteroid Administration in Patients with CNS Tumour Pseudo-progression.

In patients under treatment for brain tumours, worsening of pre-existing neurological focal deficits, suggesting tumour progression or recurrence, can be accompanied by neuroradiological appearances of oedema and/or a contrast enhancing lesion within the tumour bed. However, this radiological pattern is not necessarily associated with disease progression and can be related to immunological changes associated with treatment. This section discusses the management of patients who show clinical and/or radiological manifestations that can relate to this phenomenon of pseudo-progression.

For symptomatic patients, dexamethasone is the most commonly used corticosteroid in this context (Kall, 2004; Dietrich, 2011). The aim of this treatment is to attenuate clinical manifestations (in particular associated sign and symptoms of increased cranial pressure. Several clinical studies have shown that dexamethasone can inhibit maturation of dendritic cells and subsequently their potential for antigen presentation, dexamethasone can also impair natural-killer-cell activity. Therefore, dexamethasone doses and duration of therapy should be limited to the minimum amount needed to control neurologic symptoms. All CNS disease progression will be assessed using iRANO criteria (see *Section 10.8*), which accounts for CNS tumour pseudo-progression.

It is unclear the extent to which pseudo-progression may occur in non-CNS conditions. For this reason, investigators are encouraged to continue the administration of nivolumab while waiting for a repeat tumour assessment, at least 4 weeks apart, in the event of radiological evidence of progressive disease but stable clinical status. Administration of corticosteroids in case of pseudo-progression in non-CNS conditions should be discussed with the Study Chair or Co-chair. All solid tumour progression will be assessed using iRECIST criteria (see *Section 10.2*), which accounts for immunotherapeutic effects during treatment with ICIs, such as nivolumab.

## 6.10 Immunotherapy Continuation Pending Confirmation of Progression

A decision of whether a patient should continue immunotherapy pending confirmation of radiographic disease progression should be established based on perceived benefits and risks as per the response criteria outlined in *Section 10*.

Continuation of immunotherapy might be considered pending follow-up imaging as long as patients are deriving apparent clinical benefit with minimal and acceptable toxic effects.

Immunotherapy should be interrupted for patients who require treatment with corticosteroids for evolving symptoms associated with cerebral oedema or who have more than mild treatment-related toxic effects such as at least grade 2 immune-related adverse events. Resumption of immunotherapy may be considered when symptoms resolve, steroids are reduced and the gadolinium enhancing tumour burden is classified as stable disease, partial response, or complete response on a follow-up scan, or when relevant treatment-related toxic effects have resolved to grade 1 or less or pre-treatment baseline. Decision to continue/discontinue immunotherapy should be made after discussion with the Study Chair or Co-chair.

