#### **5.3** Criteria to Resume Treatment

Patients may resume treatment with study drug when the drug-related AE(s) resolve to Grade ≤1 or baseline value, with the following exceptions:

- Patients may resume treatment in the presence of Grade 2 fatigue;
- Patients who have not experienced a Grade 3 drug-related skin AE may resume treatment in the presence of Grade 2 skin toxicity;
- Patients with baseline Grade 1 AST/ALT or total bilirubin who require dose delays for reasons other than a 2-grade shift in AST/ALT or total bilirubin may resume treatment in the presence of Grade 2 AST/ALT or total bilirubin;
- Patients with combined Grade 2 AST/ALT and total bilirubin values meeting discontinuation parameters should have treatment permanently discontinued;
- Drug-related pulmonary toxicity, diarrhea, or colitis, must have resolved to baseline (Grade 1) before treatment is resumed. Patients with persistent Grade 1 pneumonitis after completion of a steroid taper over at least 1 month may be eligible for retreatment following discussion with the Study Chair or Co-Chair;
- Patients with drug-related endocrinopathies adequately controlled with only physiologic hormone replacement may resume treatment following discussion with the Study Chair or Co-Chair.

If the criteria to resume treatment are met, the patient should restart treatment at the next scheduled time point as per protocol. However, if the treatment is delayed past the next scheduled time point as per protocol, this time point should become day one of the subsequent cycle. If treatment is delayed or interrupted for > 6 weeks, the patient must be permanently discontinued from protocol therapy.

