## 10.9 Response Criteria for Target Lesions

Response criteria are assessed based on the product of the longest diameter and its longest perpendicular diameter. Development of new disease or progression in any established lesions is

considered PD, regardless of response in other lesions - e.g., when multiple lesions show opposite responses, the progressive disease takes precedence.

For patients with early progressive imaging findings (within six (6) months from initiation of the immunotherapy), including patients who develop new lesions but who do not have substantial neurological decline, confirmation of radiographic progression by follow-up imaging should be sought three (3) months after initial radiographic evidence of progressive disease to decrease the likelihood of prematurely declaring progressive disease in patients with pseudo-progression or delayed response.

Imaging within the 3-month follow-up can be done as medically appropriate at the discretion of the treating physician.

Patients with confirmation of further radiographic progression based on a comparison with the scan that first showed evidence of disease progression (new reference scan) should be classified as having progressive disease with the date of disease progression back-dated to the first date that the patient met criteria for radiographic progression. In those patients, non-responsiveness to treatment should be assumed and therapy discontinued.

Patients who develop substantial new or worsened neurological deficits not due to comorbid events or a change in co-administered medication at any time within the 3-month follow-up window should be designated as non-responsive to treatment and should discontinue immunotherapy. For these patients, the date of actual tumour progression should also be backdated to the date when radiographic progressive disease was initially identified.

If follow-up imaging does not confirm further disease progression compared with the scan of the tumour that first showed initial progressive changes, but instead there is stabilization or reduction in tumour burden, treatment should be continued or resumed in the absence of increased corticosteroid dosing.

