## 10.9.2 Confirmation of Radiographic Progression

Traditional imaging criteria to define PD may be less reliable and could lead to premature discontinuation of potentially beneficial therapy. Early increases in lesion size or new lesions do not define PD unless further progressive changes are confirmed upon follow-up imaging, provided that patients are not experiencing clinical decline. Particularly for indications such as glioblastoma, where effective therapeutic interventions are limited, and durable responses are elusive, continuation of immunotherapies beyond initial progression may lessen the likelihood of prematurely discontinuing potentially effective therapy (Okada, 2015; Bouffet, 2016).

Spider-plots describing changes in tumor volume over time for solid tumor patients undergoing immune checkpoint blockade demonstrate that early progressive radiographic findings typically stabilize or improve within three months for the majority of patients who ultimately derive clinical benefit (Topalian, 2012; Hamid, 2013; Brahmer, 2012). Based on these observations, among patients with early progressive imaging findings including the development of new lesions who are not experiencing significant neurologic decline, confirmation of radiographic progression via follow-up imaging should be sought no sooner than three months after initial radiographic evidence of PD is detected, to decrease the likelihood of prematurely declaring PD in patients with pseudo-progression or delayed response. Imaging within the three (3)- months follow-up period can be performed as medically appropriate at the discretion of the treating clinician. Among those with confirmation of further radiographic progression based on comparison to the scan which first revealed evidence of progression, or who exhibit significant clinical decline at any time, should be classified as PD with the date of disease progression backdated to the first date that the patient met criteria for radiographic progression. Such patients should be discontinued from their current immunotherapy regimen.

If follow-up imaging does not confirm further progression compared to the scan which first revealed initial progressive changes, but instead reveals stabilization or reduction in tumor burden, in the absence of increased corticosteroid dosing, treatment should be continued or resumed (see *Figure 4*).

[figure not shown]

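### A CNS patient held for steroid-treated oedema until the three-month confirmation scan is told to resume by 10.9 and 10.9.2, but 5.3 permanently discontinued that patient at six weeks

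*Protocol*

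**What the plan says.** Four parts of the Protocol bear on a CNS patient whose treatment is held around a first progressive scan.

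- **Section 6.10 (hold).** "Immunotherapy should be interrupted for patients who require treatment with corticosteroids for evolving symptoms associated with cerebral oedema"
- **Section 6.10 (resumption).** Treatment may restart once the symptoms have settled and the steroid dose is lower, provided that on imaging the "gadolinium enhancing tumour burden is classified as stable disease, partial response, or complete response on a follow-up scan". A separate branch covers treatment-related toxicity that has resolved. No interval is given for the scan. The decision is to be discussed with the Study Chair or Co-Chair.
- **Section 5.3 (maximum hold).** "If treatment is delayed or interrupted for > 6 weeks, the patient must be permanently discontinued from protocol therapy". No exception is written for CNS tumours or for suspected pseudo-progression.
- **Section 10.9 (confirmation).** For progressive imaging within six months of starting, without substantial neurological decline, "confirmation of radiographic progression by follow-up imaging should be sought three (3) months after initial radiographic evidence of progressive disease". Section 10.9.2 words the interval as a minimum: it "should be sought no sooner than three months after initial radiographic evidence of PD is detected". If the follow-up scan shows stabilisation or shrinkage instead, 10.9 says "treatment should be continued or resumed in the absence of increased corticosteroid dosing", and 10.9.2 agrees.

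Both 10.9 and 10.9.2 also let the treating physician image earlier within those three months. Routine disease evaluations are at the end of cycle 1 and every two months, each with a window of minus 7 days (Section 8.2, footnote 12).

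**The concern.** An instruction to resume can apply only to a patient who has been held, and 6.10 orders a hold for steroid-treated oedema. Section 6.10 concerns continuation pending confirmation of progression and defers to the response criteria of Section 10. The only follow-up interval that Section 10 fixes for CNS confirmation is three months or more, which is longer than the six-week maximum in 5.3.

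The protocol anticipates this situation. Section 6.9.2 is devoted to steroid use in CNS pseudo-progression, and the brain-tumour eligibility criterion raises debulking to lower the risk of toxicity from it. If the rules conflict, whether such a patient stays on drug depends on which section a site follows and whether it happens to order an early scan. That affects exposure and could affect whether a response is recorded for the primary ORR, in cohorts of at most 20 and 30 patients with success cut-offs of 5 and 6 responses.

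**Working it through.** The plan gives no figure to reproduce. The check is calendar arithmetic, assuming 1 month = 365.25/12 = 30.44 days.

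**Inputs**
- Maximum interruption (5.3): 6 weeks = 6 × 7 = 42 days.
- Confirmation scan (10.9, 10.9.2): 3 months = 3 × 30.44 = 91.3 days = 13.0 weeks.
- Routine scan gap (8.2): two months, taken as 56 days (two 28-day cycles) to 2 × 30.44 = 60.9 days, less up to 7 days for the window.
- Steroid rule (10.11): an MRI cannot be read as CR, PR or SD if corticosteroids were increased within two weeks (14 days) of it, relative to the dose at the prior assessment.

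**1. Hold from the first progressive scan to the three-month scan.** 13.0 − 6 = 7.0 weeks past the limit. If burden is then stable or lower and steroids are not increased, 10.9 and 10.9.2 say resume. Under 5.3 the patient was permanently off protocol therapy 7 weeks earlier. Both instructions cannot be followed.

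**2. Hold from the first progressive scan to the next two-monthly scan.** Earliest: 56 − 7 = 49 days, or 60.9 − 7 = 53.9 days. Nominal: 56 to 60.9 days. All exceed 42. The excess runs from 49 − 42 = 7 days to 60.9 − 42 = 18.9 days, about 1 to 3 weeks.

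**3. Hold starting at the end-of-cycle-1 scan.** If the two months run from treatment start, the next routine scan is 56 − 28 = 28 to 60.9 − 28 = 32.9 days later, inside the limit. If they run from the cycle-1 scan, step 2 applies. The wording does not settle which.

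**4. Hold starting between scans.** The trigger in 6.10 is steroid need for symptoms, not a scan date, so the next routine scan may fall within 42 days.

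**5. Discretionary early scan.** It is allowed at any time. If the last steroid increase is on the day of the hold, 10.11 rules out an SD, PR or CR reading for 14 days, leaving 42 − 14 = 28 days in which a qualifying reading is possible. Any later increase shortens that period. Table 10 adds that PR and SD need a stable or decreased steroid dose.

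**6. Other limits on the same event.** If it is classed as drug-related toxicity, shorter limits apply. Section 6.2 removes patients whose non-haematological toxicity needs more than 7 days' delay. Section 6.9.1 discontinues for Grade 2 neurological toxicity lasting more than 7 days. Neither is cross-referenced to 6.10.

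**The case against.** The strongest reply is that a condition for resuming plus a maximum hold is not in itself a contradiction: the patient resumes if the condition is met in time. Section 6.10 does not name the three-month scan. That interval exists to avoid declaring progression too early, and earlier imaging is expressly permitted in both 10.9 and 10.9.2. This stands, and it rules out two stronger readings that a reader might infer:

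- That resumption under 6.10 must wait for the three-month scan. No section says so.
- That the resume path cannot be used. An early scan can meet the condition inside 42 days, and so can a routine scan when the hold starts between assessments.

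The affected group is also limited. The three-month rule covers progression within six months of starting without substantial neurological decline; 10.9 discontinues patients with substantial new or worsened deficits not explained by comorbidity or medication change. Table 11 allows clinically stable patients to stay on treatment pending confirmation, so a three-month hold is not the default course.

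Nor do the documents show that PFS handling turns on an early scan: confirmed progression is back-dated to the first progressive scan either way.

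What the reply does not remove is the wording of 10.9 and 10.9.2, which directs resumption after imaging set at three months or more, while 5.3 has already ended treatment. It might be said that 5.3 concerns recovery from drug-related events, but its six-week sentence carries no such restriction. The Study Chair discussion in 6.10 is not stated to override it.

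**Conclusion.** The concern holds in a limited form. A CNS patient interrupted under 6.10 at first radiographic progression and held until the three-month scan receives opposite instructions, with 5.3 having ended treatment about 7 weeks before 10.9 and 10.9.2 direct resumption. When the hold starts at a progressive scan, resumption within six weeks generally depends on a discretionary scan not scheduled for this purpose, since the next two-monthly scan is about 1 to 3 weeks too late.

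This assumes that the hold begins at the progressive scan, that two months means 56 to 61 days counted from that scan, and that 5.3 applies to all interruptions, as worded. It does not extend to every interrupted CNS patient. The documents do not say how many patients would be affected, so the effect on ORR is possible but cannot be sized. The point is worth correcting before sites have to interpret it; it does not undermine the design.

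**What to change.** Reconcile 5.3, 6.10, 10.9, 10.9.2 and 10.11 so that the protocol states one consistent rule on two matters: how the maximum interruption applies to a CNS patient held pending iRANO confirmation, and which scan, read under what steroid conditions, governs resumption. Say also how the seven-day rules in 6.2 and 6.9.1 apply when the same event is classed as drug-related toxicity; otherwise the conflict moves to those sections. The clinical team must decide the rule, and this review takes no view on which interval is right.

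The cost is amended wording and cross-references. No new procedure is needed if the earlier imaging already allowed is used; naming a scan for this purpose would add at most an entry to the Section 8.2 calendar.

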#### **6.11 Dose Modifications for Endocrine Adverse Events**

Endocrine	Management/Next Dose of Nivolumab				
Hypophysitis; Adrenal					
Insufficiency					
≤Grade 1	Continue protocol therapy.				
Grade 2	• Off protocol therapy, unless exception in Section 6.2 is met				
	(Grade 2 hypothyroidism, thyroiditis and thyroid dysfunction				
	adequately managed with thyroid hormone replacement).				
Grade 3	Off protocol therapy.				
Grade 4	Off protocol therapy.				

Note: All patients with symptomatic pituitary enlargement, exclusive of hormone deficiency, but including severe headache or enlarged pituitary on MRI should be considered Grade 3 events. Isolated thyroid or testosterone deficiency may be treated as Grade 2, if there are no other associated deficiencies and adrenal function is monitored.

Please evaluate pituitary function before beginning steroid therapy or replacement therapy of any kind.

Recommended management: See Endocrine AE Management Algorithm (see Section 6.11.1).

## 6.11.1 Recommended Endocrine Adverse Event Management Algorithm

Consider visual field testing, endocrinology consultation, and imaging if clinically indicated.

Toxicity (CTCAE v.4.03)	Management	Follow-up			
Asymptomatic TSH elevation	
 
Continue protocol therapy
 
If TSH < 0.5 x LLN, or TSH > 2 x ULN, or consistently out of range in 2 subsequent measurements: include fT4 at subsequent cycles as clinically indicated;
 
Consider endocrinology consult.
 
	• N/A			
Symptomatic Endocrinopathy	
 
Evaluate endocrine function;
 
Consider pituitary scan.
 
Symptomatic with abnormal lab/pituitary scan:
 
Hold nivolumab infusion;
 
1-2 mg/kg/day methylprednisolone IV or PO equivalent;
 
Initiate appropriate hormone therapy*
 
No abnormal lab/pituitary MRI scan but symptoms persist:
 
Repeat labs in 1-3 weeks/ MRI in 1 month and consult endocrinology.
 
	If improves (with or without hormone replacement):  • Taper steroids over at least 1 month;  • Consider prophylactic antibiotics for opportunistic infections;  • Resume nivolumab therapy as per protocol;  • Patients with adrenal insufficiency may need to continue steroids with mineralocorticoid component.			
Suspicion of adrenal crisis (e.g. severe dehydration, hypotension, shock out of proportion to current illness)	
 
Discontinue protocol therapy;
 
Rule out sepsis;
 
Stress dose of IV steroids with mineralocorticoid activity;
 
IV fluids;
 
Consult endocrinologist;
 
If adrenal crisis ruled out, then treat as above for symptomatic endocrinopathy.
 
	• N/A			

Patients on IV steroids may be switched to an equivalent dose of oral corticosteroids (e.g. prednisone) at start of tapering or earlier, once sustained clinical improvement is observed. Lower bioavailability of oral corticosteroids should be considered when switching to the equivalent dose of oral corticosteroids.

\* For symptomatic hypothyroidism, nivolumab should be withheld, and thyroid hormone replacement should be initiated as needed. For symptomatic hyperthyroidism, nivolumab should be withheld and methimazole should be initiated as needed. Corticosteroids at a dose of 1 to 2 mg/kg/day methylprednisolone equivalents should also be considered if acute inflammation of the thyroid is suspected. Upon improvement, nivolumab may be resumed after corticosteroid taper, if needed. Monitoring of thyroid function should continue to ensure appropriate hormone replacement is utilized.

For symptomatic **adrenal insufficiency**, nivolumab should be withheld, and physiologic corticosteroid replacement should be initiated as needed. Monitoring of adrenal function and hormone levels should continue to ensure appropriate corticosteroid replacement is utilized.

For symptomatic **hypophysitis**, Nivolumab should be withheld, and hormone replacement should be initiated as needed. Corticosteroids at a dose of 1 to 2 mg/kg/day methylprednisolone equivalents should also be considered if acute inflammation of the pituitary gland is suspected. Upon improvement, Nivolumab may be resumed after corticosteroid taper, if needed. Monitoring of pituitary function and hormone levels should continue to ensure appropriate hormone replacement is utilized.

For symptomatic **diabetes**, nivolumab should be withheld, and insulin replacement should be initiated as needed. Monitoring of blood sugar should continue to ensure appropriate insulin replacement is used.

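### Section 6.11.1 lists treatment-dose methylprednisolone without condition for symptomatic endocrinopathy, while its own footnote limits that dose to suspected thyroid or pituitary inflammation

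*Protocol*

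**What the plan says.** The symptomatic row of the table in section 6.11.1 opens with a work-up, including "Consider pituitary scan". For a symptomatic patient with an abnormal laboratory result or scan it then lists three steps: hold nivolumab, "1-2 mg/kg/day methylprednisolone IV or PO equivalent", and start hormone therapy. The asterisk to the footnote is on the hormone step alone. On improvement, the follow-up column says "Taper steroids over at least 1 month".

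The row is not confined to the pituitary. Its follow-up column adds "Patients with adrenal insufficiency may need to continue steroids with mineralocorticoid component", and the adrenal-crisis row sends patients back to it: "If adrenal crisis ruled out, then treat as above for symptomatic endocrinopathy".

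The footnote goes condition by condition. In thyroid disease the 1 to 2 mg/kg/day dose "should also be considered if acute inflammation of the thyroid is suspected". In hypophysitis it "should also be considered if acute inflammation of the pituitary gland is suspected". For adrenal insufficiency, "physiologic corticosteroid replacement should be initiated as needed". For diabetes it gives insulin and glucose monitoring and mentions no steroid.

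**The concern.** The row and its footnote give different steroid rules for the same symptomatic patients. The row ties the dose to neither an organ nor suspected inflammation; the footnote ties it to both. Because the asterisk is on the hormone step, nothing marks the steroid step as qualified by the text below.

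What is at stake is patient safety and consistency between sites. The trigger is symptoms plus an abnormal laboratory result, so ordinary symptomatic hypothyroidism meets it. Read literally, the row gives that child treatment-dose steroid and then a taper of at least a month. Section 1.6.6 reports opportunistic infections in rare cases of prolonged high-dose corticosteroid or other immunosuppressant treatment, none of them in this study's patients at the time of writing.

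**Working it through.** No arithmetic applies. The check sets the texts side by side and asks whether another section settles the difference.

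**Step 1: row against footnote on the 1 to 2 mg/kg/day dose (section 6.11.1).**

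| Symptomatic condition | Row, if laboratory result or scan is abnormal | Footnote |
|---|---|---|
| Hypothyroidism, hyperthyroidism | listed, no condition | consider, if acute thyroid inflammation is suspected |
| Hypophysitis | listed, no condition | consider, if acute pituitary inflammation is suspected |
| Adrenal insufficiency | listed, no condition | physiologic replacement; this dose not named |
| Diabetes | not named in the row | insulin; no steroid named |

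The two agree only where thyroid or pituitary inflammation is suspected, and even there the footnote says consider. Diabetes is the weakest line, since neither the row's work-up nor section 7.10 names it. The thyroid and adrenal lines do not depend on it.

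**Step 2: which rule the rest of the protocol supports.**
- Section 6.2 exempts Grade 2 hypothyroidism, thyroiditis and thyroid dysfunction from removal when thyroid hormone replacement controls them. Section 6.11 repeats the exemption.
- Section 7.10 lets Grade 2 hypothyroidism controlled in that way continue on therapy.
- Section 5.3 allows treatment to resume, after discussion with the Study Chair or Co-Chair, where physiologic replacement alone controls the endocrinopathy. This is weaker support, because a patient could reach that state after a taper.

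The thyroid passages in sections 6.2, 6.11 and 7.10 do not mention treatment-dose steroid. They fit the footnote and not the row.

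**Step 3: whether any text says which rule governs.**
- Section 6.11 asks for pituitary evaluation before any steroid or replacement.
- Section 7.10 asks for an endocrinologist.
- Section 7.13 asks that subspecialty consultation be considered, particularly when systemic immune suppression is in view.
- Section 7.14 ties corticosteroids to severity and calls for consulting the Study Chair or Co-chair.

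Each makes an automatic steroid less likely. None says whether the row or the footnote decides the steroid step.

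**The case against.** The best defence is that the footnote is simply the row's organ-by-organ detail. It sits directly under the table, repeats the row's dose, covers withholding nivolumab as well as hormones, and names each condition a site would look up. The algorithm is headed as recommended, and the consultation requirements above surround it. This stands as a reason to rate the risk low. It does not remove the difference, because the link to the footnote is on the hormone step and no text gives the footnote precedence.

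A second defence is that the protocol often writes discretionary steroids tersely, and that is true. Section 6.7.1 gives a bare dose for Grade 2 pneumonitis where section 7.5 says consider. Section 6.13.1 does the same for raised creatinine where section 7.12 says consider. In section 6.4.1 a merely considered steroid for Grade 1-2 rash is followed by an unqualified taper. So although the endocrine row uses Consider for the scan, a reader who infers that the bare steroid step cannot be shorthand goes too far. The unqualified taper line likewise proves little.

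A reader might also infer that the protocol leaves no route to replacement-only management. Sections 6.2, 6.11 and 7.10 describe that route for thyroid disease.

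Finally, the proposed wording could be said to make a clinical choice by softening the row for pituitary disease. It uses the footnote's own condition, and steroid stays available whenever inflammation is suspected.

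**Conclusion.** The point holds as a modest patient-safety inconsistency that should be corrected. The row lists treatment-dose methylprednisolone without condition; its footnote makes that dose conditional for thyroid disease and hypophysitis, and does not name it for adrenal insufficiency or diabetes. The thyroid provisions elsewhere support the footnote as the intended rule. This rests on reading the row literally, as a site might.

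The size cannot be given in patients, because the protocol states no expected frequency of symptomatic endocrinopathy. Counting the footnote's conditions would measure neither patients nor risk.

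A reader might infer an effect on study removal, the objective response rate or the Simon two-stage design, since sections 6.2 and 10.11 contain rules that depend on steroid or immunosuppressive use. The documents do not support going that far. They give no rate of such events, and they do not say that a step listed in a recommended algorithm makes immunosuppression required in the sense of section 6.2. No such effect is claimed.

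**What to change.** Make two edits in the symptomatic row of section 6.11.1:

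1. Reword the steroid step as: Consider "1-2 mg/kg/day methylprednisolone IV or PO equivalent" if acute thyroid or pituitary inflammation is suspected, with a pointer to the footnote.
2. Move the asterisk from the hormone step to the branch heading, so that the footnote governs the whole branch. The adrenal-crisis row, which refers back, then inherits the same condition.

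Adding *if given* to the taper line is an optional conforming edit.

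The cost is a few words in one table row, with no added procedures, patients or data. The clinician must judge whether inflammation is suspected before giving the dose, which the footnote already asks for in thyroid disease and hypophysitis.
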